## Study Summary

Title	Use of continuous glucose monitoring system with intensive feedback in adolescents with poorly controlled type 1 diabetes
Short Title	Use of continuous glucose monitoring system with intensive feedback in adolescents with poorly controlled type 1 diabetes
Protocol Number	16-01011
NCT Number	NCT03020069
Principal Investigator	[name]
Methodology	Randomized open label
Study Duration	Estimated duration for the main protocol (e.g. from start of screening to last subject processed and finishing the study)
Study Center(s)	Single-center or multi-center. If multi-center, note number of projected centers to be involved.
Objectives	to determine if using a glucose sensor helps adolescents with t1D understand their range of options in controlling their diabetes
Number of Subjects	60
Diagnosis and Main Inclusion Criteria	Adolescents with type 1 diabetes and an HbA1c $\geq 8\%$

CONFIDENTIAL

This material is the property of the NYU School of Medicine and Langone Medical Center. Do not disclose or use except as authorized in writing by the study sponsor

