#### SUBJECTS:

Sixty adolescents, ages 13-22 years, with type 1 diabetes and an HbA1c  $\geq 8\%$  who are also naive to CGMS or who have not used a CGMS in at least six months use will be recruited from the diabetes outpatient population followed at Bellevue Hospital, Lutheran Hospital, Woodhull Hospital, and the NYU Fink Pediatric Ambulatory Care Center. Forty subjects will be randomly assigned to the CGMS group and 20 subjects will be assigned to the control group.

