#### ANALYSIS:

Measures of the level of glycemic control will be assessed primarily by HbA1c and secondarily by the average glucose tests results on the patient's glucose meter. Comparison of the glucose results (average, range, standard deviation, number of daily tests) between the study entry, 1 week, 1 month and 3 month follow up visits will be done. Comparison of HbA1c at entry and at 3-month follow-up will be performed. Questionnaire scores will be compared between study entry, 1 week follow up, 1 month follow up and 3-month follow-up visits for DES and Stages of Change scales. We will determine if there is a correlation between the scores on the questionnaires and measures of glucose control. We will classify study and control participants into adherent and non-adherent groups.

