#### CONFIDENTIAL

This material is the property of the NYU School of Medicine and Langone Medical Center. Do not disclose or use except as authorized in writing by the study sponsor

Use of continuous glucose monitoring system with intensive feedback in adolescents with poorly controlled type 1 diabetes  
Version Date: 04/26/2018

Dichotomizing participants into adherent and non-adherent:

Study subjects will receive points for calibrating the CGM device and for successfully completing phone contact with the pediatric diabetes team. The patient will receive 2 points for calibrating the device 2 times/day for at least 5 days, 1 point for calibrating the device 2 times on at least 3 days and 0 points for calibrating any less. Similarly the patient will receive 2 points for completing successful phone contact with study personnel for at least 5 days, 1 point for completing phone contact on at least 3 days and 0 point for contact any less than mentioned before. The two scores will be added to get a total score. Patients with scores 3-4 will be classified as adherent and scores 0-2 will be classified as non-adherent. Control subjects who complete 4 or more phone calls on different days will be classified as adherent and those who complete fewer phone calls will be classified as non-adherent.

Statistical methods:

Demographic data will be tabulated. Statistical analysis of questionnaires will be done according to published standards. The paired t-test will be used for comparisons involving stages of change score.

Independent variables will include the empowerment score, average glucoses, HbA1c and whether the subjects fall into the adherent vs. non-adherent groups. Dependent variables include glucose level(s) and stage of change. We will analyze the 7 day average glucose by meter download and categorize the results in terms of change: No change (-15 to + 15), Higher ( $\geq + 15$ ) or Lower ( $\leq -15$ ). We will analyze the HbA1c and categorize the results in terms of change: No change ( $> -0.5$  to  $+ 0.5$ ), Higher ( $\geq + 0.5$ ) or Lower ( $\leq -0.5$ ). Stages of change (Appendix A) will be categorized as unchanged, improved or worsened. In addition, descriptive statistics including quality of life, diabetes knowledge scale, and demographic variables will be tabulated.

Statistical Analysis for sensor study:

Questionnaires:

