Daily Phone Log: (Appendix H): Scoring will be done for each day of the initial week of the study, in both CGM intervention group, and control group based on the following: Study subjects will receive points for calibrating the CGM device and for successfully completing phone contact with the pediatric diabetes team. The patient will receive 2 points for calibrating the device 2 times/day for at least 5 days, 1 point for calibrating the device 2 times on at least 3 days and 0 points for calibrating any less. Similarly the patient will receive 2 points for completing successful phone contact with study personnel for at least 5 days, 1 point for completing phone contact on at least 3 days and 0 point for contact any less than mentioned before. The two scores will be added to get a total score. Patients with scores 3-4 will be classified as adherent and scores 0-2 will be classified as non-adherent. Control subjects who complete 4 or more phone calls on different days will be classified as adherent and those who complete fewer phone calls will be classified as non-adherent.

The distribution of the data will be assessed using the Kolmogorov-Smirnov test. All categorical variables will be presented as mean +standard deviation. For categorical variables the differences between the compliant and non-compliant groups will be assessed using the Mann Whitney or rank order Wilcoxon test based on normality. For categorical variables independent sample t test will be used. Univariate analysis will be used to establish correlation between variables of interest.

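### The only outcome form specified for HbA1c, the first-ranked glycaemic measure, is a three-way change category; no between-group test or covariate adjustment for entry HbA1c is stated

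*Combined protocol and SAP*

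**What the plan says.** The ANALYSIS section sets the ranking: "Measures of the level of glycemic control will be assessed primarily by HbA1c and secondarily by the average glucose tests results". It then adds: "Comparison of HbA1c at entry and at 3-month follow-up will be performed". No test is named for that comparison. It is not said to be categorised, and it is not said to be made between the randomised groups.

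The Statistical methods give one form for HbA1c as a result: "We will analyze the HbA1c and categorize the results in terms of change". The categories are No change, Higher and Lower, cut at 0.5 points in each direction. No test is attached to them. The same paragraph sorts the variables: "Independent variables will include the empowerment score, average glucoses, HbA1c and whether the subjects fall into the adherent vs. non-adherent groups", and then "Dependent variables include glucose level(s) and stage of change". HbA1c is therefore listed as an independent variable and is not named as a dependent one.

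Entry HbA1c is measured on every participant (METHODS, phase 1), but no analysis uses it as a covariate. The only modelling language comes in the last paragraph of the statistical text: "Univariate analysis will be used to establish correlation between variables of interest". The named group tests in that paragraph contrast compliant with non-compliant participants, not the randomised groups. On size, SUBJECTS states: "Forty subjects will be randomly assigned to the CGMS group and 20 subjects will be assigned to the control group".

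**The concern.** Grouping a continuous laboratory value into three bands discards information wherever the limits are drawn. A fall of 0.6 and a fall of 3.0 points count the same. An unadjusted change score is also less efficient than a model with the entry value as a covariate, because participants who start high tend to fall more and the change score over-corrects for that.

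With 40 and 20 participants there is little information to spare. Counts by category also do not estimate how large the effect on HbA1c is. Nothing in the plan commits to a between-group HbA1c difference with a confidence interval.

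This is separate from the band limits touching at exactly +0.5, a value that falls in both No change and Higher. Well-drawn bands would lose the same information.

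**Working it through.** **No stated figure to reproduce.** The documents give 60 participants without derivation, and no power, alpha, effect size, SD, correlation or dropout.

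**Inputs from the documents.** 40 CGMS and 20 control (SUBJECTS); category cuts at -0.5 and +0.5 (Statistical methods); HbA1c at entry and 3 months (METHODS, phases 1 and 4).

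**Assumed inputs.** Two-sided alpha 5%; normally distributed change, equal variances at the two times, no dropout; SD of change 0.5 to 2.0, with 0.8 to 1.5 as the central range; entry-to-3-month correlation r from 0.5 to 0.9. The comparison between randomised groups is itself assumed, because the plan names none.

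**Step 1: the cut alone.** With three ordered categories and no mean shift, the efficiency relative to the continuous change is 2φ(h)²/(1−Φ(h)), where h = 0.5/SD of change. For SD 1.2, h = 0.417, φ(h) = 0.366 and 1−Φ(h) = 0.339, so efficiency is 2 × 0.366²/0.339 ≈ 0.79 and the loss is about 21%.

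| SD of change | 0.5 | 0.8 | 1.0 | 1.2 | 1.5 | 2.0 |
|---|---|---|---|---|---|---|
| Loss from the cut | 26% | 19% | 20% | 21% | 23% | 26% |

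Sixty participants then carry the information of about 44 to 49.

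**Step 2: unadjusted change against covariate adjustment.** The efficiency of the change score relative to a model adjusted for entry is (1+r)/2. The loss is 25% at r = 0.5, 15% at 0.7, 10% at 0.8 and 5% at 0.9.

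**Step 3: both together.** Combined loss = 1 − (step 1 efficiency) × (1+r)/2.

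| SD of change | r = 0.5 | r = 0.7 | r = 0.8 | r = 0.9 |
|---|---|---|---|---|
| 0.8 | 39% | 31% | 27% | 23% |
| 1.0 | 40% | 32% | 28% | 24% |
| 1.2 | 41% | 33% | 29% | 25% |
| 1.5 | 42% | 35% | 31% | 27% |

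The range is 23% to 42%, or about a quarter to two fifths.

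**Step 4: power, by formula.** Power ≈ Φ(d/SE − 1.96), with SE = SD of change × √(1/20 + 1/40). For SD 1.2, SE = 0.329. With d = 0.8, d/SE = 2.43.
- Continuous change: Φ(2.43 − 1.96) = 68%.
- Adjusted for entry, r = 0.7: 2.43/√0.85 = 2.64, giving 75%.
- Three ordered categories: 2.43 × √0.79 = 2.16, giving 58%.

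For d = 0.5 the three figures are 33%, 38% and 27%.

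**Step 5: simulation.** HbA1c SD 1.6 at each time and r = 0.7, which makes the SD of change 1.6 × √(2 × 0.3) = 1.24; 40:20; 3,000 or more trials per setting. Figures are approximate, and repeat runs agreed to about one percentage point.

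| True difference | Adjusted for entry | t-test on change | Rank test on categories | Chi-square on categories |
|---|---|---|---|---|
| 0.8 | 70% | 64% | 53% | 45% |
| 0.5 | 34% | 31% | 25% | 21% |

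Converting the 0.8 row to information: ((1.96 + z(0.53))/(1.96 + z(0.70)))² = (2.035/2.484)² = 0.67, a loss of 33%. This agrees with step 3 at r = 0.7.

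**The case against.** **The categories may not be the main HbA1c analysis.** The sentence on categories can be read as two steps, analyse and then categorise. The entry-to-3-month comparison in ANALYSIS may be continuous. The closing statistical paragraph, though garbled, plans normality testing, means with SDs and t-tests, which are methods for numeric data. A reader might infer that the HbA1c result will be nothing but a table of counts; the documents do not establish that. This part stands, and the loss is therefore conditional on the categories carrying the between-group comparison. It does not supply the missing analysis: the entry-to-3-month sentence names no test, and as worded it need not use the control group at all.

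**The tests compared above are not in the plan.** This also stands. No test on the categories and no between-group HbA1c test is specified, so the actual loss cannot be fixed. An unordered chi-square would lose more than the ordered figures.

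**The entry value is used.** A reader might infer that HbA1c is never corrected for its starting level. A change score subtracts that level; what is absent is covariate adjustment. Nor is chance imbalance at entry as harmful as it first looks. With SD 1.6, the SE of the entry difference is 1.6 × √(1/40 + 1/20) = 0.438, so an imbalance above 0.5 points has a probability of about 25%. Only (1 − r) of it carries into a change-score comparison: at r = 0.7, 0.3 × 0.5 = 0.15 points.

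**HbA1c is not the trial's central outcome.** The AIM concerns motivation and behaviour, and the first rank applies only among glycaemic measures. No document supports a 0.8-point effect, and at 0.5 points power is low under every method. This limits the importance of the point but is no reason to prefer the less efficient analysis.

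**Conclusion.** The point holds as a conditional one. The only specified outcome form for HbA1c is a three-way category, and neither a continuous between-group comparison nor covariate adjustment for the entry value is stated. If the categories carry the comparison between groups, the cut alone costs about 19-26% of the information (SD of change 0.5 to 2.0). The cut plus an unadjusted change score costs about 25-40% relative to a continuous baseline-adjusted analysis (r about 0.5-0.9, SD of change about 0.8-1.5).

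A reader might take a quarter to two fifths as the cost of categorising, or as an established property of this trial. It is neither: it combines two separate losses and rests on an SD and a correlation that the documents do not give. Categorised change was the weaker analysis in every setting computed; only the size of the loss is uncertain. The change should be made.

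**What to change.** In the Statistical methods, replace the sentence on HbA1c categories with wording such as: *3-month HbA1c will be analysed as a continuous value in a linear model with assigned group and entry HbA1c, and reported as an adjusted difference between groups with a 95% confidence interval. Counts of Higher, No change and Lower will be given by group as description only.* List 3-month HbA1c among the dependent variables, so that the variable list agrees.

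The meter average should also stay continuous and be adjusted for its entry value. Because it is followed at 1 week, 1 month and 3 months, it needs a method suited to repeated visits, such as a mixed model, and not the single-endpoint model used for HbA1c.

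For HbA1c the cost is one degree of freedom for the entry value. The change is to analysis wording, with no new data, visits or participants.

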#### CONFIDENTIAL

This material is the property of the NYU School of Medicine and Langone Medical Center. Do not disclose or use except as authorized in writing by the study sponsor

Use of continuous glucose monitoring system with intensive feedback in adolescents with poorly controlled type 1 diabetes  
Version Date: 04/26/2018

appointments and staff will determine if they are interested in participation in the study using a recruitment script uploaded under recruitment materials section.

The study is minimal risk (MR). The device is approved by the FDA and is being used according to its cleared/approved labeling. The probability and magnitude of harm or discomfort anticipated in this research is similar to those ordinarily encountered in daily life or during the performance of routine physical or psychological examinations or tests.

The use of the CGMS will be described.

The study will consist of 4 phases.

1: For all participants at entry into the study the participant's HbA1c will be measured in the lab at the location of the patient's visit and his/her glucose meter will be downloaded as part of routine care. The average capillary glucose level, (with range and standard deviation) and the average number of tests per day over the prior 14 days will be recorded. The current individual care plans for self-management of type 1 diabetes will be reviewed by the study personnel with the participant.

Questionnaires will be administered to all the participants except Appendix F:

- 1) Appendix A - Stages of Change measure (original). We created a 5 item questionnaire to assess the patient's current stage.
- 2) Appendix B - Psychosocial self-efficacy (University of Michigan Diabetes Research and Training Diabetes Empowerment Scale short-form) - DES. 8 items. Also available for use.(3-6)
- 3) Appendix C - Knowledge and risk perception (University of Michigan Diabetes Research Training Center Diabetes Knowledge Scale). 23 items - DKT. We are substituting rapid acting insulin for NPH insulin in item 17 since NPH is not used in our study population. Available for use without permission as long as the source is quoted.(7, 8)
- 4) Appendix D - Quality of life (Peds QL 3.2, Diabetes module,) – Peds QL. 33 items on a Likert scale.(9)

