Demographics (Appendix G): data will be put in table form, with range, mean, s.d. scores for age; % Male/Female; and descriptive data for the remainder of the items. In Questions #11, 13 and 14, with 1-5 scales, the range, mean, and s.d. scores will be given. Stages of Change (Appendix A): scores can be given categorically, with each question assigned a score of 1 for a “yes” answer, and zero for a “no” answer; then range, mean, s.d. will be calculated before and after the intervention. In addition, a “yes” or “no” answer to these questions will determine which “stage of change” category the subject belongs in, according to the definition of “stages of change”. This is categorical data. We will analyze movement in the “stages of change” by comparing the score before and after the study intervention. This will be categorical: improvement, no change, deterioration.

CONFIDENTIAL

This material is the property of the NYU School of Medicine and Langone Medical Center. Do not disclose or use except as authorized in writing by the study sponsor

Use of continuous glucose monitoring system with intensive feedback in adolescents with poorly controlled type 1 diabetes  
Version Date: 04/26/2018

Diabetes Empowerment Scale-Short Form (Appendix B): the average of the scores of the completed items will be tabulated. Each question is answered as 1-5, and there are 8 questions. Thus, the scores can range from 1-5. The scores will be compared before and after study intervention.

Diabetes Knowledge Test (Appendix C): There are 23 multiple choice questions, scored as correct or incorrect. This will be administered only at baseline.

Peds Quality of Life 3.2 Diabetes Module: (Appendix D): There are 33 questions with Likert scale answers (0-4). Scores are transformed on a scale of 0-100. This test will be administered before and after the study intervention.

PHQ-2: (Appendix E): The score ranges from 0-6. The scores will be compared before and after the study intervention.

CGM Satisfaction Scale: (Appendix F): We are using an abbreviated version of a previously published CGM-SAT scale. Each question is scored 1-5 and the mean is calculated. This will be given after the intervention and only in the intervention group.

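### Stage of change is analysed as improved, unchanged or worsened, with a paired before/after score, and neither analysis adjusts for entry stage or names a test between arms

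*Combined protocol and SAP*

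**What the plan says.** The AIM section hypothesises that short-term CGM use with feedback, together with self-efficacy, will influence stage of change. Stage is measured in all participants at entry, 1 week, 1 month and 3 months with a purpose-built instrument: "We created a 5 item questionnaire to assess the patient's current stage".

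The ANALYSIS section treats it in two ways.

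- **Category.** Under Statistical methods: "Stages of change (Appendix A) will be categorized as unchanged, improved or worsened". The Questionnaires paragraph on Appendix A repeats the rule: "We will analyze movement in the “stages of change” by comparing the score before and after the study intervention", and then "This will be categorical: improvement, no change, deterioration".
- **Score.** The same paragraph scores each item 1 for yes and 0 for no, and summarises range, mean and s.d. before and after. Statistical methods adds: "The paired t-test will be used for comparisons involving stages of change score".

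Stage is an outcome: "Dependent variables include glucose level(s) and stage of change". The predictors listed beside it do not include entry stage: "Independent variables will include the empowerment score, average glucoses, HbA1c and whether the subjects fall into the adherent vs. non-adherent groups". The closing paragraph of the ANALYSIS section names only univariate analysis for relating variables, and the only groups it names for a group test are compliant and non-compliant participants. Allocation is described in SUBJECTS: "Forty subjects will be randomly assigned to the CGMS group and 20 subjects will be assigned to the control group". No stratification by stage is stated, and no eligibility rule restricts entry stage.

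**The concern.** A three-class change variable on a bounded ordered scale is limited by where the participant begins. Someone who enters at the top can only be unchanged or worsened, so keeping the best stage counts the same as remaining at the worst. Someone who enters at the bottom can only be unchanged or improved. A move of one stage and a move of several stages fall in the same class.

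The class counts therefore mix response with the entry-stage distribution. Two things follow if they are used to compare groups. Between the randomised arms, a real effect is diluted, and a chance difference in entry stage shifts the counts in a trial with only 20 controls. Between adherent and non-adherent participants, who are not formed by randomisation, entry stage may be related both to adherence during the first week and to later stage, so it can confound the comparison.

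**Working it through.** The plan states no power, alpha, effect size, correlation or stage distribution, so there is no planned figure to reproduce. Appendix A is not in the text, so the number and definition of stages cannot be checked. From the documents: arms of 40 and 20, and five yes/no items, so the score is bounded between 0 and 5. Everything else below is an assumption.

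**1. Chance imbalance in the share at the top stage.** With true share p in both arms, SE = √[p(1 − p)(1/40 + 1/20)]. For p = 0.30 this is √(0.21 × 0.075) = 0.125, so 95% of chance differences lie within ±1.96 × 0.125 = ±0.246. Exact binomial probabilities of a gap in either direction:

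| Share at top | 95% range (normal approx.) | P(gap ≥ 15 points) | P(gap ≥ 20 points) |
|---|---|---|---|
| 10% | ±16.1 points | 9% | 2% |
| 20% | ±21.5 | 21% | 9% |
| 30% | ±24.6 | 27% | 14% |
| 40% | ±26.3 | 31% | 16% |

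**2. Effect on the improved share.** If t is the share at the top and q the chance of improving among those able to, the observed improved share is q(1 − t).

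- No true effect, with 10% of controls and 30% of the CGM arm at the top. For q = 0.3: 0.27 v 0.21, a spurious 6 points. For q = 0.5: 0.45 v 0.35, a spurious 10 points.
- True effect q = 0.3 v 0.6 with equal top shares. The difference is 30 points at t = 0; 0.48 − 0.24 = 24 points at t = 0.2; 0.36 − 0.18 = 18 points at t = 0.4.
- The same effect with unequal top shares. Controls 10%, CGM 30%: 0.42 − 0.27 = 15 points. Controls 30%, CGM 10%: 0.54 − 0.21 = 33 points.

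**3. Does adjustment change error rates or power?** Two simulation models were used, with five assumed stages, 40 v 20 and two-sided 5%. The unadjusted analysis is a Mann-Whitney test between arms on the three-class change.

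- *At most one stage of movement* (30% v 60% chance of moving up, 15% of moving down). The adjusted analysis is a linear model on arm and entry stage, with indicators for the top and bottom stages. Here change equals follow-up minus entry stage, so modelling either gives the same arm effect. Type I error was 0.048 to 0.050 unadjusted and 0.051 to 0.056 adjusted. Power was 0.304 unadjusted v 0.277 adjusted with 20% at the top, and 0.205 v 0.206 with 35%. There was no gain.
- *Latent normal scale cut into stages.* The adjusted analysis is a rank-based analysis of covariance of follow-up stage on arm and entry stage. Type I error was 0.04 to 0.06 for both. With an effect of 0.8 SD and 30% at the top, power was 0.43 v 0.76 at entry-to-follow-up correlation 0.3, 0.56 v 0.82 at 0.5, and 0.71 v 0.90 at 0.7; repeat runs agreed within about 3 points. With 10% at the top and correlation 0.5 it was 0.67 v 0.86. At correlation 0.85 the gain fell to about 3 to 9 points, and at an effect of 0.4 SD to about 1 to 12 points.

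So the gain runs from none to about 30 points. The gain of 19 points with only 10% at the top shows that much of it comes from using the full scale with a baseline covariate, not from the ceiling alone.

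**The case against.** The best defence is that the category is not the whole analysis. The item score is summarised before and after and tested, and it keeps the size of a move. That stands, and it rules out a reading that entry data serve only to form the three classes. It does not answer the point: the paired test works within participants, the score is bounded too, and it has no entry-stage term.

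Second, randomisation balances entry stage in expectation. That also stands. A reader might infer that the arm comparison is biased; the simulations show type I error near 5% with or without adjustment.

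Third, a reader might take one of the simulated powers, such as 56%, as the power of the trial's stage analysis. The documents do not support that. They name no test between arms for stage, so the figure belongs to no planned analysis, and it depends on an effect, a correlation and a stage distribution that the plan does not give. The share at the top could be small in a group selected for HbA1c of 8% or more; if it were 5%, a gap of 15 points or more would arise in only about 2% of trials.

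Fourth, a reader might infer that a covariate removes the ceiling. It does not. Follow-up stage has the same top, and a participant who enters there still cannot show benefit.

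**Conclusion.** The point holds in a limited form. For an outcome named in the hypothesis, the plan collects entry stage from everyone, adjusts for it nowhere, and names no comparison of randomised arms. The three-class summary discards the size of movement and lets the entry-stage mix shape the counts.

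Its size depends on the unknown share at the extremes. For 10% to 40% at the top, a gap between arms of 15 points or more has a 9% to 31% chance. A 20-point gap would create a spurious difference of 6 to 10 points in the improved share when 30% to 50% of those able to improve do so. With 20% to 40% at the top in both arms, a true 30-point difference among those able to improve appears as 24 to 18 points.

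Between randomised arms this is dilution and chance imbalance. In the adherent versus non-adherent comparison it is possible confounding, whose direction and size cannot be judged from the documents. The case for change rests on a comparison that is conditional on entry stage and uses the whole scale. It does not rest on a promised gain in power, and no single power figure should be quoted.

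**What to change.** In the ANALYSIS section, under Statistical methods and in the Appendix A paragraph of the Questionnaires part:

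- Compare the randomised arms on follow-up stage on its full ordered scale, with arm and entry stage as covariates. Use a proportional-odds model, or a rank-based analysis of covariance if cells are sparse. Make 3 months the main time point and analyse 1 week and 1 month in the same way.
- Include entry stage in the adherent versus non-adherent comparison of stage.
- Keep the improved/unchanged/worsened table as description, cross-tabulated by entry stage and arm, so that top-stage and bottom-stage entrants are visible.
- State in advance when the rank-based fallback applies and how adjacent stages would be merged.

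The cost is wording only. Entry stage is already collected, and no visit, measurement or participant is added. The downsides are the proportional-odds assumption and, with 20 controls spread over several stages, the likely need to merge some of them.
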